6.10.2 Blinding

It is not possible to blind this study due to the nature of reporting the MRIs, whereby comparison is made with the previous images, which indicates the trial arm the participant has been randomised to.

6.11 Data Collection, Management and Analysis

6.11.1 Data Collection Methods

Each participant will be given a unique trial Participant Identification Number (PIN), this will consist of the centre number and participant number (sequential). Data will be collected at the time-points indicated in the Trial Schedule (section 6.6).

The method of data collection is direct online entry of data onto the central database, stored on servers based at NCTU. This will be carried out by members of the trial team working within each research site. Data may be entered onto paper Case Record Forms (CRFs) prior to entry onto the database (but this is not an essential step). Staff will receive training on data collection and use of the online system.

X-ray images taken at baseline, remission and six month follow up will be transferred from site to the sponsor for analysis using the NHS Image Exchange Portal (IEP) or discs. All images will be anonymised by the site prior to transfer.

Data collection, data entry and queries raised by a member of the CADOM trial team will be conducted in line with the NCTU and trial specific Data Management Standard Operating Procedure.

Identification logs, screening logs, enrolment logs and tapes of qualitative interviews will be kept at the trial site in a locked cabinet within a secured room.

Clinical trial team members will receive trial protocol training. All data will be handled in accordance with the Data Protection Act 1998.

6.11.2 Data Management

Data will be entered in the approved CADOM database by a members of the trial team at each site and protected using established NCTU procedures.

Data will be entered under the participants PIN number onto the central database stored on the servers based at NCTU. Access to the database will be via unique, individually assigned (i.e. not generic) usernames and passwords, and only accessible to members of the CADOM trial team at NCTU, and external regulators if requested. The servers are protected by firewalls and are patched and maintained according to best practice. The physical location of the servers is protected physically and environmentally in accordance with University of East Anglia's General Information Security Policy 3 (GISP3: Physical and environmental security).

The database will be developed by NCTU Data Management, in conjunction with the CADOM trial team. The database software provides a number of features to help maintain data quality, including;

maintaining an audit trail, allowing custom validations on all data, allowing users to raise data query requests, and search facilities to identify validation failure/ missing data.

After completion of the trial the database will be retained on the servers of NCTU and the sponsor servers for the X-ray images for on-going analysis of secondary outcomes.

The identification, screening and enrolment logs, linking participant identifiable data to the pseudoanonymised Participant Identification Number, will be held locally by the trial site. This will either be held in written form in a locked filing cabinet or electronically in password protected form on hospital computers. After completion of the trial the identification, screening and enrolment logs will be stored securely by the sites for 15 years

6.11.3 Non-Adherence and Non-Retention

The consent form will explain that if a participant wishes to withdraw from the study, the data acquired prior to that point will be retained, unless the patient requests otherwise. Reason for withdrawal will be recorded, if given, as will loss to follow up.

6.11.4 Statistical Methods

6.11.4.1 Statistical Analysis Plan

A full Statistical Analysis Plan (SAP) will be developed between the trial statistician and Chief Investigator and agreed with the trial's management group prior to analysis

The feasibility measures will be presented as point estimates with 95% confidence intervals. There is no intention, at this stage, for any formal comparative analyses regarding these measures, though levels of missing data will be explored with respect to certain baseline characteristics, e.g. age, measures of disease severity.

Estimates of outcome variability (e.g. the standard deviation) will be made with 95% confidence intervals to help inform future sample size calculations. Any between group efficacy analyses are exploratory only. The suggested primary efficacy outcome measure, days with immobilisation, will be analysed using a Cox regression model. Regression models with appropriate error terms (e.g. Normal or Poisson distributions) will be applied to the secondary outcomes.

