There are no existing qualitative studies that have been undertaken exploring the patients experience and perspectives on the management of CN. It is difficult to make direct comparisons from the published literature on the impact of a diagnosis of CN on the patient. There is evidence that CN has a negative effect on quality of life (QoL)⁴³, compared to those with uncomplicated diabetes but also in comparison to those with chronic heart failure and Parkinson's disease⁴⁴. In one small study it was suggested that the health status in CN patients was comparable to that following minor lower extremity amputation³⁰. Assessing the impact of CN on QoL is important to help establish the optimal methods of treatment and timing of intervention. There are currently no validated disease specific patient reported outcome measures (PROMs) for CN. A systematic review on measures of health related quality of life (HRQoL) could not recommend a specific tool for use in diabetes related foot disease⁴⁵. The most widely used tool was the SF-36, although current research into diabetic foot disease favours the use of SF-12 as it is shorter yet valid alternative to the SF-36 which is considered by many researchers as too long to administer to studies with large samples such as a future definitive RCT. A recent study comparing the outcomes of SF-12 and SF-36 in patients with diabetic foot disease found substantial agreement when comparing the component score for each tool⁴⁶. In England the National Institute for Health and Care Excellence (NICE) favours the EQ-5D. However the use of this particular measure in the treatment of CN may be limited as the actual treatment of immobilisation and rest reduces mobility one of the 5 key components of the

EQ-5D. The systematic review specifically recommended a more detailed analysis of QoL measures in CN⁴⁵.

The aim of this study is to explore the use of serial MRI in an attempt to reduce the duration of immobilisation of the foot and thereby reduce the morbidity associated with its routine management and reduce costs. The project will have two components: a feasibility study and embedded within this a qualitative study of the patient's perspective of the experience of being diagnosed with CN and undergoing treatment.

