6.4.1 Arm A (Intervention – Standard Care and Serial MRIs)

Immobilisation discontinued on the basis of MRI defined disease resolution at 3, 6, 9 or 12 months

In the intervention arm participants will receive additional MRIs at 3, 6, 9 and 12 months. Patients randomised to serial MRI will not undergo further MRI once remission has been diagnosed i.e. if remission is diagnosed at 6 months the MRI at 9 and 12 months will not occur.

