6.4.2 Arm B (Control – Standard Care and one additional MRI)

Immobilisation discontinued on the basis of clinical remission determined by skin temperature measurement and MRI. In the standard care arm participants will receive one additional MRI when the temperature measurements, X-ray and/or signs and symptoms indicate to the clinical team that the foot is in remission.

A temperature difference of $\leq 2^{\circ}\text{C}$ which is maintained or improves on two separate consecutive occasions for a period of ≥ 4 weeks will be the indicator to arrange the second MRI, to confirm the diagnosis of remission.

If participants in either arm of the trial have not reached remission at the end of the 12 month active phase of the study they will exit the study. Ongoing standard care will be provided by their clinical team.

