6.5.2 Exploratory Clinical Outcomes

- Days with immobilisation, measured at the end study
- Progression of foot deformity as documented by measuring radiological foot alignment angles. All x-rays will be taken in a weight bearing position with standard views as per WPD. Comparison from baseline, diagnosis of remission, and six months after remission. The angles that will be assessed are:
 - Calcaneal Inclination – the angle formed by the horizontal and a line from the base of the heel and inferior cortex of the calcaneus
 - Talar Declination – the angle between the line originating from the centre of the talus bisecting the talar neck and head and the weight bearing plantar surface from the calcaneus to the 5th metatarsal
 - Talo-first metatarsal angle – the angle between the line originating from the centre of the talus bisecting the talar neck and head, and the line through the longitudinal axis of the first metatarsal.

- Hindfoot-forefoot angle - the angle between the talocalcaneal bisector and the second metatarsal shaft
- Cuboid height (mm) - the distance from the plantar aspect of the cuboid to a horizontal line drawn from the plantar calcaneal tuberosity to the fifth metatarsal head.

Patients who have undergone previous minor amputation and/or previous orthopaedic surgical fixation of the foot altering/removing the anatomical landmarks of the foot will be excluded from this analysis due to the absence of bony landmarks.

At each study visits the following will be measured and recorded on the eCRF:

- Number of new ulcerations on the index foot
- Number of new ulcerations on the contralateral foot
- Number of new infections on the index foot
- Number of new infections on the contralateral foot
- Number and severity of falls (Hopkins Fall Grading System)¹
- Number of minor and major amputations on the index foot at the end of the follow up phase of the study
- Number of minor and major amputations on the contralateral foot at the end of the follow up phase of the study
- The number of participants in each arm requiring further intervention for CN (e.g. further immobilisation) within 6 months of remission

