6.11.4.2 Study Outcomes

Feasibility measures

- Number of eligible patients recruited, recruitment and retention levels, willingness of clinicians to participate in the study, and dropout rates.

Efficacy outcomes

- Days with immobilisation, for the intervention versus standard care will be measured
- Number of foot ulcers, infections, falls, minor and major amputations from randomisation to the end of the study
- Progression of foot deformity from randomisation – remission, and at the end of the study.
- Changes in psychological health status assessed by the Hospital Anxiety and Depression Scale (HADS) from baseline at, 3, 6, 9 and 12 months, remission and at the end of the study period.
- Changes in health related quality of life assessed by the Medical Outcomes Short-Form Health Questionnaire (SF12) from baseline at, 3, 6, 9 and 12 months, remission and at the end of the study period.
- Changes in reported pain experienced in the foot, ankle or leg as reported on a Visual Analogue Scale (VAS) from baseline at, 3, 6, 9 and 12 months, remission and at the end of the study period.

Economic Evaluation of resource use

- Collected through a patient diary

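### Cox regression is the only between-arm analysis named for days with immobilisation; its event is undefined and its hazards are unlikely to be proportional, so a difference in days should be reported beside it

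*Protocol*

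**What the plan says.** **Analysis.** Protocol section 6.11.4.1: "The suggested primary efficacy outcome measure, days with immobilisation, will be analysed using a Cox regression model". The Normal and Poisson models in that section are for secondary outcomes, and the standard deviation is descriptive. Between-group efficacy analyses are declared exploratory. The event for the Cox model is not stated.

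**Outcome.** It is a quantity of days: "Days with immobilisation, measured at the end study" (6.5.2) and "Days with immobilisation, for the intervention versus standard care will be measured" (6.11.4.2). The aim in 5.1 is to "reduce the duration of immobilisation of the foot and thereby reduce the morbidity associated with its routine management". The trial summary (1.3) wants an effect size to plan a definitive trial.

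**Stopping.** Arm A (6.4.1): "Immobilisation discontinued on the basis of MRI defined disease resolution at 3, 6, 9 or 12 months"; the timeline in 6.6 puts these scans at weeks 12, 26, 40 and 52. Arm B (6.4.2) needs a temperature criterion that is "maintained or improves on two separate consecutive occasions" over at least four weeks, with fortnightly visits (6.7.2).

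**Restarting.** Off-loading resumes after relapse in either arm (6.7.4) and after an arm B MRI that does not show remission (6.7.2). Section 6.5.2 captures this only as "The number of participants in each arm requiring further intervention for CN (e.g. further immobilisation) within 6 months of remission".

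**Leaving.** Participants who "have not reached remission at the end of the 12 month active phase of the study they will exit the study" (6.4.2). Follow-up otherwise ends six months after each participant's own remission (6.7.4). Section 6.11.5 sets a complete-case analysis without imputation.

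**The concern.** A hazard ratio for stopping does not measure days immobilised. The two come apart here for two reasons.

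- **Different stopping grids.** Arm A can stop on scan days only, if 6.4.1 is taken as written. Arm B can stop at many dates but waits out a hold. The ratio of stopping rates then changes over the year for reasons unrelated to disease.
- **Restarts.** If the undefined event is first discontinuation, a participant who stops early, relapses and is immobilised again counts as an early success. The additional days are lost.

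At stake is the between-arm effect estimate carried forward to plan a definitive trial.

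Separately, the stop date itself is unclear, and every estimator needs it. Section 6.4.1 has MRI-defined resolution, whereas 6.7.2 allows MRI and/or clinical findings. Sections 5.1.1 and 6.7.2 read as arm B stopping before its confirming MRI; 6.4.2 and 6.7.4 read as stopping after it.

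**Working it through.** The protocol gives no figure to reproduce: 60 participants comes from funder guidance (6.8), with no power calculation.

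**Inputs from the protocol:** median time to remission 9 to 12 months (5.1), taken as 274 and 365 days; scans at days 84, 182, 280 and 364 (6.6); 14-day visits; 28-day hold; 30 per arm. **Assumed:** Weibull shape 1, 1.5 or 2.5; MRI wait 0, 7 or 14 days; the same resolution-time distribution in both arms.

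**Rules.** Arm A stops at the first scan on or after resolution. Arm B stops at the next fortnightly visit + 28 days + MRI wait. The horizon is day 364, with 18 scenarios and Cox fitted with Efron ties.

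**1. One scenario by hand** (median 365, shape 2.5, wait 14). S(t) = 0.5^((t/365)^2.5) gives S(84) = 0.9825, S(182) = 0.8854, S(280) = 0.6996, S(364) = 0.5024.
- Arm A stopped before day 364: 1 - 0.6996 = 30.0%; including day 364: 1 - 0.5024 = 49.8%.
- Arm B lags by 28 + 14 = 42 days. Stopped before day 364: 1 - S(308) = 1 - 0.6355 = 36.5%; including day 364: 1 - S(322) = 1 - 0.6025 = 39.8%.
- Mean days, arm A: 84 + 98 × 0.9825 + 98 × 0.8854 + 84 × 0.6996 = 325.8. Arm B: 42 + 14 × ΣS(14k), k = 0 to 22, = 326.3. Difference (A minus B) -0.4 day.

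Counting day-364 stops puts arm A ahead; not counting them puts arm B ahead. Mean days do not change, because a stop on day 364 contributes 364 days either way. The simulated hazard ratios are 1.27 and 0.83.

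**2. All 18 scenarios.**

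| Setting | Hazard ratio (A v B) | Mean days, A minus B |
|---|---|---|
| 28-day hold, day-364 stops are events | 1.01 to 1.29 | -1.5 to +8.7 (closed form -0.7 to +8.3) |
| Same, day-364 stops not events | 0.73 to 0.94 | unchanged |
| No hold (published times already include it) | about 0.8 to 1.0 | about +10 to +28 |

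In the first row the hazard ratio is 1.12 to 1.86 up to day 182 and 0.88 to 1.18 afterwards, so hazards are not proportional although the disease is identical.

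**3. Restarts** (assumed relapse 20 to 30% in A v 10% in B, 84 to 168 days each). A first-stop hazard ratio is unchanged by construction; total days to month 12 move by +1 to +9. If the event were final discontinuation, 30% v 10% relapse moves the ratio from 1.04-1.05 to 0.82-0.93.

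**4. Sampling error at 30 per arm.** Still immobilised at 12 months (exponential): 0.5^(12/9) = 0.40 to 0.5^(12/12) = 0.50, so about 36 to 30 events. The 95% limits multiply and divide the hazard ratio by exp(1.96 × 2/√36) = 1.92 to exp(1.96 × 2/√30) = 2.05. For mean days the half-width is t(58) × SD × √(2/30) = 0.517 SD, i.e. ±31 to ±62 days for an assumed SD of 60 to 120.

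**5. Handling of incomplete follow-up.** Counting early leavers at their observed time (assumed 20% in A, 10% in B) turned a true +7 days into -12 to -14. Dropping non-remitters as incomplete cases turned -14.2 into +7.3 (median 274, assumed 60-day temperature lag, 20% restarts in arm A only). A days estimate therefore needs explicit rules.

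**The case against.** Cox is a reasonable choice when about half the participants may still be immobilised at 12 months: it handles that censoring, and a naive mean of days does not. The protocol never says the event is first discontinuation, and a statistical analysis plan not shown here may define it, including the rule for stops on the last scan. Much of the gap between hazard ratio and days comes from that one boundary day. Section 6.11.4.1 also does not say that the standard deviation to be estimated is for immobilised days. All of this stands, and it is why Cox should be kept.

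It does not remove the point. A summary that crosses 1 according to how one day is treated, while mean days do not move, needs a days-scale estimate beside it.

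Two stronger readings are tempting and are not supported:
- **That the hazard ratio is biased in one direction.** Step 2 gives ratios on both sides of 1. If arm A may also stop on the standard-care rule, one reading of 6.7.2, the ratio is 1.08 to 1.29 with -7 to -2 days, so the direction agrees.
- **That re-immobilised days can never enter a Cox analysis.** That holds for a first-discontinuation event. Step 3 shows that they enter if the event is final discontinuation.

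The stop-date contradiction affects every estimator and is no argument for one over another.

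**Conclusion.** The point holds as a minor one. The only named between-arm analysis has no defined event, is not expected to have proportional hazards under the two stopping schedules, and does not report the outcome on its own scale. With identical disease, a hazard ratio of about 1.0 to 1.3 goes with about -2 to +9 days; the ratio becomes about 0.7 to 0.95 if week-52 scan stops are not events; with no hold it is about 0.8 to 1.0 with +10 to +28 days. These figures rest on assumed Weibull shapes and MRI waits, on arm A stopping only at scans, and on the protocol's 9 to 12 month median. Direction depends on those assumptions. The distortion is small against 95% limits of roughly ×/÷1.9 to 2.05 on the hazard ratio, in an analysis declared exploratory. Confidence is medium.

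**What to change.** In 6.11.4.1:
- Report the between-arm difference in mean immobilised days from randomisation to a fixed 12-month horizon, with a 95% CI, adjusted for centre and including re-immobilised days.
- Count participants followed to 12 months without remission up to the horizon; do not drop them as incomplete cases under 6.11.5.
- Treat those who leave before 12 months (alternative diagnosis, withdrawal, transfer, loss to follow-up, death) as censored, for example with a restricted-mean or inverse-probability-of-censoring-weighted estimate. Do not count them at their observed time.
- State that days after the six-month post-remission visit are unobserved and taken as zero, with a sensitivity analysis.
- Keep Kaplan-Meier curves and Cox alongside, with the event defined and a stated rule for stops on the 12-month scan.

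Reconcile 6.4.1 with 6.7.2, and 5.1.1 and 6.7.2 with 6.4.2 and 6.7.4, because they set the stop date. No clinical rule is proposed here.

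Cost: a few sentences and slightly more analysis. No visits are added, since treatment is already recorded on the eCRF (6.4.5). There are two downsides. The estimate is specific to its horizon, because about 24 to 61% are not in remission at 12 months in the simulation. The zero-days assumption also falls unequally: 2 to 19% of arm A and 5 to 30% of arm B stop before week 26, so their last trial visit precedes month 12.

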6.11.4.2 Study Outcomes

Feasibility measures

- Number of eligible patients recruited, recruitment and retention levels, willingness of clinicians to participate in the study, and dropout rates.

Efficacy outcomes

- Days with immobilisation, for the intervention versus standard care will be measured
- Number of foot ulcers, infections, falls, minor and major amputations from randomisation to the end of the study
- Progression of foot deformity from randomisation – remission, and at the end of the study.
- Changes in psychological health status assessed by the Hospital Anxiety and Depression Scale (HADS) from baseline at, 3, 6, 9 and 12 months, remission and at the end of the study period.
- Changes in health related quality of life assessed by the Medical Outcomes Short-Form Health Questionnaire (SF12) from baseline at, 3, 6, 9 and 12 months, remission and at the end of the study period.
- Changes in reported pain experienced in the foot, ankle or leg as reported on a Visual Analogue Scale (VAS) from baseline at, 3, 6, 9 and 12 months, remission and at the end of the study period.

Economic Evaluation of resource use

- Collected through a patient diary

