6.4 Interventions - Arm A and Arm B

All patients will attend the secondary care clinic for fortnightly visits or as per current standard care, outlined in 6.4.5. Additional visits maybe arranged depending on clinical need. Procedures which are part of standard care will be completed according to trial specific WPD.

In this trial a standardised assessment of serial temperature measurements will be carried out. This will be completed according to trial WPD. The temperature of both feet will be recorded at intervals of 5 minutes starting at the initial removal of the off-loading device for up to 15 minutes. This will assess acclimatisation and the period of equilibration needed for stabilisation of temperature.

- 1) Following initial removal of the off-loading device
- 2) Following a 5 minute resting period
- 3) Following a 10 minutes resting period
- 4) Following a 15 minutes resting period

The sites where the temperature will be recorded reflect the current classification tool developed by Sanders and Frykberg⁴⁸;

1. distal and proximal interphalangeal joints, metatarsophalangeal, tarsometatarsal joints
2. naviculo-cunieform joints, talo-navicular joint
3. calcaneocuboid joint
4. ankle joint, subtalar joint
5. calcaneus

One X-ray will be additional to standard care this will be taken 6 months post remission. Participants who do not reach this time point within the 18 month intervention and follow-up period will not have this X-ray. This will enable the progression of foot deformity to be assessed. If a participant becomes pregnant during the study they will not have the additional X-ray and will be excluded from the analysis of the progression of foot deformity. Two members of the research team will independently evaluate the images to assess the progression of foot deformity. Inter-rater reliability will be assessed. The X-rays will be anonymised prior to evaluation to ensure the researcher is blinded to participant number and site. [The anonymised scans will also be randomly sequenced to avoid bias.](#)

To allow comparison all X-ray and MRI images will be taken as per trial WPD.

The participants will also be asked to complete the following questionnaire/assessments. These will be completed at randomisation, 3 monthly until remission (3, 6, 9 and 12 months), 1 month after remission, and at 6 months post remission;

- 1) Pain in the foot and/or leg measured using a numerical 0-10 visual analogue scale

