6.5.3 Patient Reported Outcome Measures

The following outcomes will be collected at randomisation, and three monthly until patient is in remission. They will also be collected 1 month and 6 months post remission:

- Pain in the foot, ankle or leg measured, using the Numeric Pain Rating Scale.
- Health related quality of life assessed by the Medical Outcomes Short-Form Health Questionnaire (SF12)
- Psychological health status measured using the Hospital Anxiety and Depression Scale (HADS)
- EQ-5D-5L
- Economic Evaluation – Reported through a patient diary

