6.6 Participant Timeline

	Active Phase (fortnightly visits throughout active phase of trial)										Remission	Follow Up after remission diagnosed			
Visit Number	1		6		11		18		25			FUV1	FUV2	FUV3	FUV4
month			3m		6m		9m		12m			1month	2months	3months	6months
Week **	0	2 weekly	W12	2 weekly	26	2 weekly	40	2 weekly	52						
Check In/exclusion criteria *	*														
Hand out FIS *	*														
Consent *	*														
Randomisation *	*														
Medical History *	*														
Foot Surgical history *	*														
Medication *	*	*	*	*	*	*	*	*	*	*	*	*	*	*	*
Record any amputation/s *	*	*	*	*	*	*	*	*	*	*	*	*	*	*	*
Record any infection/s *	*	*	*	*	*	*	*	*	*	*	*	*	*	*	*
Record any ulceration/s *	*	*	*	*	*	*	*	*	*	*	*	*	*	*	*
Record any falls *	*	*	*	*	*	*	*	*	*	*	*	*	*	*	*
Hand out patient diary *	*	*	*	*	*	*	*	*	*	*	*				
Collect & upload diary *		*	*	*	*	*	*	*	*	*	*				
Foot temperatures *	*	*	*	*	*	*	*	*	*	*	*	*	*	*	*
MRI (usual care) **	*									*					
MRI (Intervention arm) **	*		*		*		*		*						
Classification *	*														
Neuropathy Assess *	*														
Vascular Assess *	*														
BMI *	*		*		*		*		*		*				*
HbA1c (use existing if <3months) *	*														
Pain VAS *	*		*		*		*		*		*				*
HADS *	*		*		*		*		*		*				*
SF-12 *	*		*		*		*		*		*				*
EQ5D *	*		*		*		*		*		*				*
Study specific X-ray															*
		← Duration of active phase of treatment will be variable →													
Patient Interviews		← →													

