6.7.3 At three, six, nine and 12 months

In addition to standard care the following questionnaires will be administered to participants in both trial arms. Health related quality of life assessed by the SF-12, Psychological health status measured using the HADs and the EQ-5D-5L. Participants will also be asked to complete a VAS to assess the pain they have experienced in their foot, ankle or leg over the last 3 months. The three monthly assessments will only continue until the patient is in remission. Once the patient is in remission they will move to the follow up phase of the study.

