6.7.4 Follow up phase

In both arms once remission is confirmed by the MRI patients will then enter a rehabilitation/weaning phase. They will be transferred into a less restrictive off-loading device and then finally into footwear as per standard care. Participants will continue to attend for monthly trial visits for 3 months to monitor for any sign of relapse. The final visits will be at 6 months post remission. Standard care will continue to be provided.

At each visit study specific procedures will be carried out:

- The temperature will be assessed as per the WPD
- The participant diary will be collected and another issued for participants to complete until their next study visit. (This is only for the first three follow-up visits)

In addition to standard care and study specific procedures the participant will be asked to complete the following questionnaires and additional tests/investigations:

Follow Up - Month 1: VAS, SF-12, HADS and EQ-5D-5L will be completed.

Follow UP Month 6: VAS, SF-12, HADS and EQ-5D-5L completed. BMI will be recorded and an X-ray of the foot and/or ankle will be taken.

Relapse will be defined as a temperature difference of $>2^{\circ}\text{C}$ compared to the contralateral foot maintained for two or more occasions or further changes on imaging¹⁵. As per standard care the final decision as to whether the participant has relapsed will be at the discretion of the clinic team. If this occurs, then the participant will then recommence off-loading with a non-removable device. They will continue to be followed up as per the study protocol.

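### The protocol contradicts itself on when HADS, SF-12, pain and EQ-5D-5L are measured around remission, and its text has no assessment to match the planned analysis at remission

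*Protocol*

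**What the plan says.** **Analysis times.** Section 6.11.4.2 lists change in "HADS) from baseline at, 3, 6, 9 and 12 months, remission and at the end of the study period". SF-12 and pain carry the same times. One month after remission is not listed, and EQ-5D-5L does not appear in that list.

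**Collection times in the text.**
- 6.4: randomisation, then "3 monthly until remission (3, 6, 9 and 12 months), 1 month after remission, and at 6 months post remission".
- 6.5.3: "The following outcomes will be collected at randomisation, and three monthly until patient is in remission", followed by "They will also be collected 1 month and 6 months post remission".
- 6.7.3: "The three monthly assessments will only continue until the patient is in remission".
- 6.7.4: "Follow Up - Month 1: VAS, SF-12, HADS and EQ-5D-5L will be completed", with the same set again at month 6.
- 6.11.5.1 repeats the post-baseline times for EQ-5D-5L.
- 6.7.2, which describes how remission is established, adds an X-ray at that point but no questionnaire.

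**Collection times in the timeline.** Section 6.6 has a Remission column, then a block headed "Follow Up after remission diagnosed" with visits FUV1 to FUV4. As extracted from the PDF, the Pain VAS, HADS, SF-12 and EQ5D rows are marked at baseline, 3, 6, 9 and 12 months, Remission and FUV4 (6 months). FUV1 (1 month) is blank. The rows are not split by arm.

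**Which one rules.** Section 6.11.1 states "Data will be collected at the time-points indicated in the Trial Schedule (section 6.6", while 6.7.4 says without qualification that the month 1 forms are completed.

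**The concern.** Three parts of one protocol give different measurement times around remission. Collection cannot be repaired afterwards: a SAP can define visit windows, but it cannot recover a form that nobody was asked to complete.

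The gap may also fall unevenly on the arms. In Arm A remission is tied to scans at 3, 6, 9 or 12 months (6.4.1), which are also the questionnaire months. In Arm B the confirming scan follows a temperature trigger that can be met at any fortnightly visit (6.4.2, 6.7.2). With complete-case analysis and no imputation (6.11.5), a comparison at remission would then rest on unequal and differently selected fractions of the two arms.

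The efficacy analyses are exploratory, but two stated aims of the study are touched. Section 6.5.1 includes the feasibility of collecting quality-of-life data, and 6.11.5.2 will report completion rates. Forms missing because the schedule disagrees with itself could be read as poor participant completion. EQ-5D-5L, which feeds the preliminary QALY estimate, has the same conflict between text and table.

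**Working it through.** The plan gives no figure to reproduce. The check sets the sections side by side and then illustrates the size of the imbalance.

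**1. Time points compared**

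| Time | Text (6.4, 6.5.3, 6.7.3, 6.7.4) | Timeline (6.6, as extracted) | Analysis (6.11.4.2) |
|---|---|---|---|
| 3, 6, 9, 12 months | yes, until remission | yes | yes |
| Remission | no | yes | yes |
| 1 month after | yes | no | no |
| 6 months after | yes | yes | as end of study |

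The text and the timeline give opposite answers at remission and at 1 month. The analysis list follows the timeline.

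**2. Position of the table marks.** Counting data columns after the row label, 12 months is column 9, Remission 11, FUV1 12 and FUV4 15. The HADS marks fall in columns 1, 3, 5, 7, 9, 11 and 15, and Pain VAS, SF-12 and EQ5D show the same pattern. The phase, visit and month header rows agree with these positions. The BMI row has the same pattern, and 6.7.4 records BMI at month 6 but not at month 1, which also suits Remission better than FUV1.

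**3. If the mark really belongs to FUV1.** The timeline would then agree with the text, and 6.11.4.2 alone would name remission. It would analyse a time with no planned collection and leave out the 1-month time that is collected.

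**4. Arm B under the text alone.** Inputs from the protocol: fortnightly visits to week 52, and questionnaires at weeks 12, 26, 40 and 52 (6.6). Assumption: remission is equally likely at each fortnightly visit from a starting week to week 52. The share that coincides is 4 divided by the number of visits.
- Weeks 2 to 52: 4/26 = 15%.
- Weeks 4 to 52: 4/25 = 16%. Arm B cannot meet its trigger before week 4, because 6.7.2 requires two readings at least four weeks apart.
- Weeks 12 to 52: 4/21 = 19%.

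So 81% to 85% of Arm B remitters would have no form at the remission visit. Even if all 30 Arm B participants remitted within 12 months, 30 × 4/26 = 4.6 to 30 × 4/21 = 5.7 would have one, about 5 or 6 people. Section 5.1 quotes a UK median time to remission of 9 to 12 months, so fewer than 30 is likely.

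**5. Using the last 3-monthly form instead.** With fortnightly visits, the longest wait since a form is from week 12 to week 24 or from week 26 to week 38, which is 12 weeks, all of it during immobilisation.

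**The case against.** The strongest reply is that the schedule governs. Section 6.11.1 points to 6.6, 6.6 marks the questionnaires at Remission without distinguishing arms, and 6.11.4.2 agrees with it. On that reading both arms are measured at remission and no imbalance arises. This part stands. It also defeats an inference that a reader might draw, that the remission measure exists in Arm A only. The documents do not support that, for three reasons:
- The table makes no split by arm.
- Even under the text, some Arm B remissions will fall on a 3-monthly visit.
- Arm A is not cleanly measured at remission either. Section 6.7.2 aligns scans with visits only if practicable, and remission is decided by the clinical team from the later report, so an Arm A form may precede that decision.

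The reply does not remove the contradiction. If the timeline governs, the 1-month assessment promised in 6.4, 6.5.3, 6.7.4 and 6.11.5.1 has no place in the schedule.

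A second reply is that the table was read from PDF. By the same column count the usual-care MRI falls in an unlabelled column between 12 months and Remission, so marks in that region may be displaced. That is a fair reason for caution about the table. It does not rescue 6.11.4.2, as step 3 of the working shows.

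A third reply is that these are exploratory outcomes in an unpowered feasibility study and that a SAP will follow. That limits the weight of the point, but a SAP does not decide which forms sites hand out.

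**Conclusion.** The point holds as an internal contradiction on measurement times. The collection text has no assessment at remission, and 6.11.4.2 analyses change at remission; that mismatch is certain. The further conflict with the timeline (Remission marked, 1 month blank) is held with moderate confidence because of the PDF extraction.

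The consequence depends on which section a site follows. Under the text, a form near remission would be much commoner in Arm A than in Arm B. The 15% to 19% for Arm B is an illustration only: it assumes equal likelihood across visits, which the protocol does not support, and treats the trigger visit as the remission date although a scan follows. Under the timeline there is no such imbalance, but the 1-month measure is lost. The protocol does not settle which applies, and the two sites could differ.

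The matter should be corrected. It does not threaten the feasibility objective as a whole, and it does not show bias between arms in the trial as conducted.

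**What to change.** Use one set of time points, the same for both arms, in 6.4, 6.5.3, 6.6, 6.7.3, 6.7.4 and 6.11.4.2, and check the EQ-5D-5L list in 6.11.5.1 against it. Either option works:

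- **(a)** In 6.11.4.2 replace remission with 1 month after remission. In the Pain, HADS, SF-12 and EQ-5D rows of 6.6, mark FUV1 and remove the Remission marks. The text already collects this time in both arms, so the cost is wording only.
- **(b)** Keep remission as an analysis time. Add a remission questionnaire for both arms to 6.4, 6.5.3 and 6.7, state which date counts as the remission assessment in each arm, and mark FUV1 in 6.6 if the 1-month measure is kept. The cost is one questionnaire set per participant.

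If collection has already finished, only the analysis times can change. In that case, report by arm and site how many forms exist at remission and at 1 month, and do not count forms that the schedule never requested as participant non-completion.
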